3. STUDY DESIGN

We will perform a Stage 2a⁴ two-arm RCT of MB-BP vs. enhanced usual care control. This is a pragmatic control group designed to inform physicians in well-resourced settings if MB-BP would be of service to refer patients to as compared to enhanced usual care patients. The study is intended to evaluate the impacts of MB-BP on the primary self-regulation outcome of interoceptive awareness (i.e. MAIA) as compared to an enhanced usual care group. Secondary self-regulation outcomes are described in the Objectives section outlined previously. This study also aims to evaluate the degree to which the engagement of MB-BP with self-regulation targets translates into improved prehypertension/hypertension medical regimen adherence, specifically for the Dietary Approaches to Stop Hypertension (DASH)-consistent diet.

The enhanced usual care control group was decided upon through recommendations by the Research Coordinating Center at Columbia University, the Data Safety Monitoring Board, and several collaborating cardiologists and family physician clinician-researchers. Enhanced usual care involves every participant being provided with a validated home blood pressure monitor (Omron, Model PB786N),¹⁷⁹ which has evidence in and of itself to potentially lower blood pressure, and is beyond usual care at this time.^{6,180} All participants who have Stage 2 hypertension (blood pressure $>140/90$ mmHg) will be offered to have their physicians notified, if not already being overseen for uncontrolled hypertension. For participants with uncontrolled hypertension who do not have a physician, we will work with participants to provide access within constraints of their health insurance. Enhanced usual care group participants receive an educational brochure from the American Heart Association entitled “Understanding and Controlling Your High Blood Pressure Brochure” (product code 50-1731).

All research assessments will take place in the Brown University Mindfulness and Cardiovascular Health Lab in Providence, RI. The MB-BP intervention classes will be offered in both a University and community-based setting.

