9. STATISTICAL CONSIDERATIONS

9.1 General Design

Analyses will evaluate (1) whether MB-BP influences self-regulation targets, (2) whether the MB-BP-induced changes in self-regulation targets are associated with changes in medical regimen adherence, and (3) whether MB-BP is associated with medical regimen adherence. Analyses will incorporate generalized linear models (GLM) with properly chosen link functions, performed using generalized estimating equations (GEE) with robust standard error estimators.^{245,246} This provides an extension of regression analysis to the case of correlated or repeated observations, allows for inclusion of both continuous and discrete dependent variables, and enables modeling of covariance structures when observations are correlated across time. Following “intention-to-treat” principles, analyses will be conducted on all participants in the randomized controlled trial, regardless of intervention completion. Analyses will use GLM with identity links for normally distributed data. The between-groups independent variable in the GEE analysis is intervention condition, with control conditions as distinct referent groups. Categorical variables will be included in GLM/GEE models as indicator variables with one level chosen as referent. Continuous independent variables such as age and baseline blood pressure would be included as linear terms. In addition, we will include assessment time as a linear term and possibly with an additional quadratic term to capture possible non-linear relationship of time with the outcomes. It is conceivable that one would observe a steeper slope in the initial months that would decrease in the pursuing months. Thus, the use of a quadratic term for assessment time would be able to capture these phenomena. To evaluate self-regulation targets as mediators of the effects of MB-BP on medical regimen adherence, mediation analyses described by Valeri and VanderWeele will be employed.²⁴⁷ Such analyses will allow for potential interactions between the exposure and mediator of interest and account for potential confounders of the exposure-mediator, mediator-outcome, and exposure-outcome relationships using standard regression techniques. These methods estimate total, indirect and direct effect sizes, as well as statistical variance.²⁴⁷

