9.2 Sample Size and Randomization

Treatment Assignment Procedures

Statistical Power:

Utilizing effect sizes and statistical variance from the Stage 1 MB-BP clinical trial showed an increase of MAIA from baseline of mean 22.6 (SD=6.5) to mean 26.3 (SD=6.0) at 6-month follow-up, demonstrating a 3.7 increase in MAIA score ($p < 0.001$). Power analyses using the T statistic and non-centrality parameter, with alpha (two-tailed) set at 0.05 and beta at 0.2, shows with a MAIA increase of 3.7 in MB-BP vs. control, sample size requirements are 46 per group. With DASH diet score increasing from 2.78 (SD=0.61) at baseline to 3.37 (SD=0.81) at 6-month follow-up in the Stage 1 MB-BP study in the 67% of participants with a low DASH score (< 5.5), demonstrating a DASH diet score increase of 0.59 ($p < 0.001$). Using an effect size of 0.5, power analyses using the T statistic and non-centrality parameter

suggest that, with alpha (two-tailed) set at 0.05 and beta at 0.2, a sample size of 33 per group will be sufficient.

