For fMRI self-regulation neural targets, resting State Functional Connectivity (rs-FC) will be expressed as correlation coefficients, transformed using Fisher's z-transformation for analysis. rs-FC will be obtained at two time points (baseline: T1; post-training: T2) for participants and controls. We will use a mixed effects model with baseline rs-FC as an additional predictor for the change outcome. There are two elements to the hypotheses – the determination of the significance of the change within group and the comparison of the change in the treatment group compared to the control group. For the comparison in change between treatment and control group, with a mixed analysis of variance (within-subjects rs-FC at T1 and T2, and between-subjects according to intervention; sample size, total n = 48, 24/group), we are able to detect an ES of 0.3 between the two treatment groups with 81.3% power (and an ES of .21 with 81.3% power for within-group mindfulness effect; an ES of 0.23 with 87.7% power for an interaction of treatment and time), with two-sided tests at alpha=0.05. Thus is reasonable power to detect small- to moderate-size differences in BOLD.²⁴⁹

Our calculations assume drop-out rates will average around 10-15% across each group, with the control group exhibiting the highest rates of withdrawal and loss to follow up. These estimates are based on the Stage 1 and 2a MB-BP trials in the UH2 phase.

Randomization procedure: Please see Section 3 (study design) above.

Blinding protocol: Please see Section 3 (study design) above.

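### The plan names neither the visit nor the model term for the primary MAIA comparison, while the sample size rests on a 6-month difference of 3.7

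*Combined protocol and SAP*

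**What the plan says.** Section 3 states the comparison: the trial is to "evaluate the impacts of MB-BP on the primary self-regulation outcome of interoceptive awareness (i.e. MAIA) as compared to an enhanced usual care group". Section 9.5.1 repeats it as a hypothesis against control, without a visit. Sections 9.3 and 9.6 only refer back to 9.1.

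Section 9.1 specifies a GEE with robust standard errors. On arm it says "The between-groups independent variable in the GEE analysis is intervention condition, with control conditions as distinct referent groups". On time it says "we will include assessment time as a linear term and possibly with an additional quadratic term", with the reason "It is conceivable that one would observe a steeper slope in the initial months that would decrease in the pursuing months". On covariates it says "Continuous independent variables such as age and baseline blood pressure would be included as linear terms". It names no arm-by-time term and does not mention baseline MAIA.

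Under the schedule in section 6.1, MAIA (listed as interoception) is measured at baseline, 10 weeks and 6 months in both arms, and at 1 year in the MB-BP arm only.

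The one time point attached to a MAIA effect is in section 9.2. The Stage 1 result was measured "at 6-month follow-up, demonstrating a 3.7 increase in MAIA score", and it is then used as a between-arm difference: "with a MAIA increase of 3.7 in MB-BP vs. control, sample size requirements are 46 per group".

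**The concern.** A primary analysis needs an outcome, a time point and a contrast. Here only the outcome and the two arms are fixed. The same GEE output could be reported as an arm main effect, an arm-by-time slope or a difference at one visit, with baseline MAIA on either side of the equation. These do not estimate the same quantity, and they can lead to different conclusions from the same data.

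The terms that are stated, arm plus time, give a between-arm difference averaged over whichever visits are in the model. If baseline is one of those visits, the average includes a point at which randomisation makes the arms equal in expectation. That is not the difference on which the sample size was based.

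The plan is more exact elsewhere. For the fMRI outcome, section 9.2 names the two scan times and baseline connectivity as a predictor, and gives power for a treatment-by-time interaction. The revision history (version 2.1) also says that the trial moved to one primary outcome to limit multiple testing. Leaving the visit and the term open gives back part of that protection.

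**Working it through.** **1. The plan's own figure.** Inputs from section 9.2: difference 3.7, SDs 6.5 and 6.0, two-sided alpha 0.05, power 80%. Root-mean-square SD = √((6.5² + 6.0²)/2) = 6.255, so d = 3.7/6.255 = 0.59. By noncentral t this needs 46 per group (power 80.1%), matching the plan. With a single SD it is 43 (SD 6.0) or 50 (SD 6.5). The 46 therefore belongs to an unadjusted comparison at one time point.

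**2. Inputs for comparing the possible tests.**
- From the documents: 50 per arm, and "Our calculations assume drop-out rates will average around 10-15% across each group". This leaves 50 × 0.90 = 45 to 50 × 0.85 = 42.5, taken as 43. SD is 6.25 and the 6-month effect is 3.7.
- Assumed, because the documents do not give them: exchangeable correlation ρ between visits of 0.3 to 0.7, a flat control mean, complete data on completers, and nominal visits at 0, 2.3 and 6 months.
- Two assumed effect patterns at (0, 2.3, 6) months: complete by 10 weeks (0, 3.7, 3.7), or growing linearly (0, 1.42, 3.7), where 1.42 = 3.7 × 2.3/6.

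**3. What each test estimates, and its standard error.** Let s = 6.25 × √(2/n). At n = 45, s = 1.318.
- (a) Arm main effect, baseline as an outcome row. This is the mean of three differences: (0 + 3.7 + 3.7)/3 = 2.47, or (0 + 1.42 + 3.7)/3 = 1.71. SE = s√((1 + 2ρ)/3). The target is the same with linear or quadratic time, because time is common to both arms.
- (b) Arm main effect, follow-up rows only: (3.7 + 3.7)/2 = 3.70, or (1.42 + 3.7)/2 = 2.56. SE = s√((1 + ρ)/2).
- (c) Arm-by-linear-time, scaled to 6 months. Mean time is 8.3/3 = 2.767; the deviations are −2.767, −0.467 and 3.233, with sum of squares 18.33. Early effect: 6 × 3.7 × (3.233 − 0.467)/18.33 = 3.35. Linear growth: 3.70. SE = 6s√((1 − ρ)/18.33).
- (d) Unadjusted 6-month t-test: 3.70. SE = s.
- (e) 6-month difference adjusted for baseline MAIA: 3.70. SE = s√(1 − ρ²).

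Worked line at n = 45, ρ = 0.5: SEs are (a) 1.08, (b) 1.14, (c) 1.31, (d) 1.32, (e) 1.14. Power (early / growing) is (a) 62% / 35%, (b) 89% / 60%, (c) 72% / 80%, (d) 79%, (e) 89%.

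**4. Results over n = 43 to 45 and ρ = 0.3 to 0.7** (power by noncentral t).

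| Test | Effect complete by 10 weeks | Effect growing linearly |
|---|---|---|
| (a) Main effect, baseline row included | 2.47, 53-72% | 1.71, 29-42% |
| (b) Main effect, follow-up rows only | 3.70, 84-93% | 2.56, 53-66% |
| (c) Arm-by-linear-time to 6 months | 3.35, 55-91% | 3.70, 64-95% |
| (d) Unadjusted 6-month t-test | 3.70, 77-79% | 3.70, 77-79% |
| (e) 6-month, adjusted for baseline MAIA | 3.70, 81-97% | 3.70, 81-97% |

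The ranking is not fixed. With an early effect, (a) has more power than (c) at ρ = 0.3 (70-72% against 55-57%), and the order reverses at ρ = 0.7 (53-54% against 89-91%). With an early effect and ρ = 0.3, (b) has more power than (e) (92-93% against 81-83%). Other trajectories would give other values, so these are not bounds.

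**The case against.** The strongest reply is that the intended analysis can be inferred. Section 9.2 points to 6 months. Section 9.1 speaks of changes induced by MB-BP and of a slope that is steeper early on, which suggests trajectories that differ by arm. That is reading (c), with a target of 3.35 to 3.70. A quadratic in time cannot be fitted to two nominal follow-up visits, which hints that baseline is an outcome row. The covariates in 9.1 are given as examples, so baseline MAIA is allowed. Sections 6.2.5 and the Protocol Summary specify a statistician blinded to allocation. The objectives also refer to a Table 1, and the revision history to a separate registration; neither is in the text available.

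Much of this stands as a limit on the point. A reader might infer that the plan tests the diluted main effect, (a). The documents do not support that: they neither state nor exclude an arm-by-time term. A reader might also infer that the analyst is free to pick a favourable result. Blinding limits directional choice, although p-values still differ by term when arm labels are masked.

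What does not stand is that inference is enough. A planning input in 9.2 does not bind the analysis in 9.1, and 10 weeks, the first visit after the course, is an equally natural primary time. The slope remark is made about time in general. A covariate that is allowed has not been prespecified.

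**Conclusion.** The gap is real and should be fixed. In the text available, the primary MAIA comparison has no visit, no tested term and no stated role for baseline MAIA, and the stated terms do not by themselves give the 6-month difference behind the sample size. Depending on the reading and the trajectory, the target runs from 1.71 to 3.70, and power from 29% to 97%.

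It would be tempting to conclude that 46 per group is wrong or that the trial is underpowered. Neither follows. The 46 is arithmetically right for the test it describes, and several readings keep most or all of the 3.7. What is missing is the link between that figure and a named test.

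The powers rest on assumed correlations, two assumed trajectories and a flat control mean. Two conclusions depend less on them. The baseline-adjusted 6-month contrast keeps the 3.7 target under both trajectories. It also has more power than the unadjusted 6-month test at every correlation tried.

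**What to change.** State in sections 9.1 and 9.5.1:

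- The primary analysis is the MB-BP minus control difference in MAIA at 6 months. This is the time point used in 9.2 and the last scheduled control visit (section 6.2.7).
- It is estimated by GEE with robust standard errors from the 10-week and 6-month visits, with arm, categorical visit, arm-by-visit and baseline MAIA. For this analysis categorical visit replaces the linear or quadratic time term; this changes the time model in 9.1 and should be stated as such.
- The randomisation factors of section 6.2.4 (age, gender, baseline blood pressure) are included, each entered once, so that category terms do not duplicate the continuous age and blood pressure terms already in 9.1.
- The 1-year MAIA values, collected only in the MB-BP arm, are descriptive and stay out of the between-arm model.

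If the team prefers another contrast, name it and restate the power for it.

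The cost is a protocol amendment with written approval from the IRB and NCCIH (section 7.4). No new data are needed.

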6.2.4 Randomization and Intervention Allocation

Randomization will occur following the completion of baseline assessments prior to the initiation of study intervention. Only individuals who complete the baseline assessments and indicate they are available for the upcoming courses will be included in the randomization process.

Stratified randomization will be used, as simple randomization can fail if it creates groups unbalanced for critical features known to affect outcomes.^{7,8} Stratified randomization can reduce both types I and II error, improve trial efficiency, and facilitate subgroup and interim analyses.⁷ Variables used to create strata include age (≤ 60 vs. > 60 years), gender (male vs. female), and/or uncontrolled hypertension (≥ 140 mmHg systolic pressure, or ≥ 90 mmHg diastolic pressure) vs. prehypertension (120 to < 140 mmHg systolic pressure, and 80 to < 90 mmHg diastolic pressure). Simple random sampling will occur within each of the eight strata, thus allowing for each arm of the study to be more balanced with respect to age, gender, and hypertension category. The total size of each stratum will vary from cohort to cohort. To conduct the randomization, a list of participant IDs and strata characteristics will be provided, and a trained researcher not affiliated with the study will perform the randomization on participants after baseline assessment and final determination of eligibility is complete. Randomization will be done using an online computer software program known as Research Randomizer (Version 4.0).⁹ The randomization process will occur after each new round of enrollment (i.e., unique cohort). If the cohort sample size is such that there are not enough participants for balance within the three strata, we will prioritize stratification by two key strata instead of three, specifically by baseline blood pressure status and gender. Furthermore, after randomization within strata, if sample sizes in the entire sample for cohort differ by more than one participant per group, then all imbalanced groups are re-randomized until the entire sample differs by no more than 1 participant per group (e.g. n=8 MB-BP, n=9 enhanced usual care control). Expected cohort sizes, consistent with the

SARP are 15-20 participants. We anticipate needing to run 6 to 7 cohorts to reach the target sample size.

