Study enrollment will continue until target enrollment goals are reached (i.e., n=50 for MBBP intervention group and n=50 for enhanced usual care control group).

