Using simulations from Fritz and MacKinnon,²⁴⁸ for 80% power to detect a mediated effect when effect of exposure on mediator, and mediator on outcome, is of small to medium strength (standardized Cohen's d effect sizes of 0.26-0.39 each), based on Sobel first-order test, we will need 90 participants. Given that 67% of Stage 1 participants had DASH diet score <5.5, recruiting a sample size of 160 participants across the UH2 and UH3 phases (Figure 1), this would allow for 107 participants with low DASH diet to be included in primary mediation analyses with DASH diet score as the outcome. Stage 1 effect sizes on DASH diet score were large Cohen's d (d=0.82). Effect sizes on the primary self-regulation outcome was medium (MAIA Cohen's d=0.59). Assuming associations between the MAIA and DASH diet score are in the small to medium range, the study should be adequately powered for mediation analyses. Please note that Stage 1 analyses also demonstrated significant improvements in other health behaviors, including alcohol consumption and physical activity following the MB-BP intervention. Secondary analyses will evaluate impacts of MB-BP on these health behaviors, but are not adequately powered for mediation analyses due to the lower proportion of participants that do not adhere to these behavioral AHA guidelines (i.e. approximately 15% of participants do not comply to AHA alcohol guidelines, and 32% do not adhere to physical activity guidelines in our Stage 1 sample).

The fMRI imaging analyses (n=24 per group) should be adequately powered, based on power calculations shown in the MINDFUL-PC study below and by power calculations outlined in the fMRI study protocol and MOP. To achieve this, we estimate having to enroll up to 60 eligible study participants into the fMRI study.

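### Section 9.1 does not commit the MAIA model to gender or randomisation cohort, although participants are randomised within both; if they are left out and shift MAIA equally in both arms, the standard error is modestly too wide

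*Combined protocol and SAP*

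**What the plan says.** **Allocation (section 6.2.4).** Strata come from age, gender and blood pressure category, and each cohort is allocated on its own: "The randomization process will occur after each new round of enrollment (i.e., unique cohort". If a cohort is too small for three factors, age is dropped, while gender and blood pressure are kept. When a cohort's arms differ by more than one participant, allocation is repeated. Six or seven cohorts of 15 to 20 people are expected, up to "n=50 for MBBP intervention group and n=50 for enhanced usual care control group". The rationale given is: "Stratified randomization can reduce both types I and II error, improve trial efficiency".

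**Analysis (section 9.1).** The model is a GEE with robust standard errors. It contains intervention condition, assessment time (linear, possibly quadratic), categorical variables as indicators (none is named) and continuous covariates: "Continuous independent variables such as age and baseline blood pressure would be included as linear terms". Sections 9.3 and 9.6 only refer back to 9.1, so no fixed covariate list appears anywhere.

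**Power (section 9.2).** The MAIA calculation is a two-group t calculation that takes no credit for covariates: "with a MAIA increase of 3.7 in MB-BP vs. control, sample size requirements are 46 per group".

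**The concern.** Stratified, balanced allocation removes the stratifying factors' contribution from the chance difference between arms. A model that omits those factors leaves the same variation in its residual, so the reported standard error exceeds the true one and the test is conservative. The efficiency that 6.2.4 gives as its reason for stratifying then does not fully reach the test.

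The named covariates also match the allocation poorly. Age is named, yet it is the factor that may be dropped. Gender is protected in the fallback, and cohort is the level at which arm sizes are forced to agree; neither is named.

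Two things are at stake. Power has little slack: 50 per arm less the 10-15% dropout in section 9.2 leaves about 42-45, against a stated need for 46. And an open list lets gender and cohort be added or left out after the data are seen, with a different standard error for the primary outcome each way.

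**Working it through.** **1. The plan's own figure.** Inputs from section 9.2: difference 3.7; SDs from "mean 22.6 (SD=6.5) to mean 26.3 (SD=6.0) at 6-month follow-up"; two-sided alpha 0.05, power 0.80. SD = sqrt((6.5² + 6.0²)/2) = sqrt(39.125) = 6.255, so d = 3.7/6.255 = 0.59, agreeing with "MAIA Cohen's d=0.59". The noncentral t calculation gives 46 per group, as stated. With SE = SD × sqrt(2/n), 50 per arm gives SE 1.251 and power 83.4%. Power is 79.3% at 45 per arm and 76.4% at 42.

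**2. Analytic scale of the effect.** If gender and cohort explain a share R² of MAIA variance, adjusted SE = 6.255 × sqrt(1 − R²) × sqrt(2/n). The documents give no R², so a range is shown for 50 per arm.

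| Assumed R² | Adjusted SE | Power | Unadjusted SE wider by |
|---|---|---|---|
| 0 | 1.251 | 83.4% | 0 |
| 2% | 1.238 | 84.1% | 1.0% |
| 5% | 1.219 | 85.2% | 2.6% |
| 10% | 1.187 | 87.0% | 5.4% |
| 20% | 1.119 | 90.6% | 11.8% |

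Subtracting 83.4% from these powers overstates the gain, because constrained allocation already shrinks the true SE of the unadjusted estimate. The comparison therefore needs simulation, against the age and blood pressure model.

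**3. Simulation with 100 participants.** Six cohorts, gender by blood pressure strata, allocation balanced within strata, arms within one per cohort, HC1 robust SE, effect 0 or 3.7, 2,500 runs. Monte Carlo error is about 0.4 points on type I error, sqrt(0.05 × 0.95/2500), and 0.7 on power, sqrt(0.85 × 0.15/2500).

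| Cohort / gender R² | Model | Mean reported SE | True SE | Type I | Power |
|---|---|---|---|---|---|
| 0 / 0 | age + BP | 1.26 | 1.26-1.29 | 5.6% | 82.8% |
| 0 / 0 | + gender, cohort | 1.26 | 1.26-1.29 | 5.6% | 83.4% |
| 5% / 2% | age + BP | 1.26 | 1.24 | 4.5% | 83.9% |
| 5% / 2% | + gender, cohort | 1.21-1.22 | 1.24-1.25 | 5.3% | 85.8% |
| 10% / 5% | age + BP | 1.26 | 1.16-1.18 | 3.7% | 85.8% |
| 10% / 5% | + gender, cohort | 1.16 | 1.16-1.18 | 5.2% | 89.2% |

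At 10%/5% the planned SE is 7-9% too wide. If allocation within strata is closer to a coin toss, which the wording of 6.2.4 does not rule out, the excess is about 4-6%.

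**4. After dropout, 88 analysed (100 × 0.88).** Against the age and blood pressure model, adding gender, blood pressure category and cohort gains about 1.5 power points at total R² 10% and about 4 at 17%, and loses about 1 at 0. With baseline MAIA also modelled (assumed correlation 0.5 with follow-up; R² 10% split 5/2.5/2.5 between cohort, gender and blood pressure category; 2,000 runs), power is 91.3% without the extra factors and 90.8% with them.

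**5. Cost under the planned standard error.** Section 9.1 states no small-sample correction. With uncorrected robust SEs and a normal reference, adding the indicators raises type I error from about 4-6% to about 7-8% at 88 analysed. It is about 8-9% at 59, the low-DASH subset (0.67 × 88 = 59).

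**6. The opposite case.** A class effect in the MB-BP arm only (assumed intraclass correlation 0.05 or 0.10) makes the age and blood pressure model's SE 7-8% or 15% too narrow, with type I error 6.8% or 9.6%. Adding gender and cohort indicators gives 7.2% or 9.8%, so they do not correct it.

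**The case against.** The best defence is that silence is not exclusion. Section 9.1 presents age and baseline blood pressure as examples, and its preceding sentence provides for categorical indicators, so gender and cohort could enter without contradicting the plan. The size rests on variance shares that no document gives. Stable cohort and gender effects are largely absorbed if baseline MAIA is modelled: at 10%/5%, the SE is then only about 2-3% too wide. Omission alone leaves a slightly conservative test, not a biased one. Adding cohort indicators under the robust SE as written would replace mild conservatism with mild anti-conservatism.

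All of this stands, and it limits the point. It does not remove it: 9.1 commits to neither gender nor cohort, nor to baseline MAIA.

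Three stronger readings are tempting and unsupported.
- A reader might infer that the plan excludes gender and cohort. It leaves them open.
- A reader might set a raw t-test against a fully adjusted model and find 80% versus 86% power at R² 20%. The plan names age and baseline blood pressure, so that comparison counts as lost some variance already covered.
- A reader might infer that the SE is too wide whenever cohort matters. That holds only for effects shared by both arms. A cohort's MB-BP participants also share a class, and an effect in that arm alone acts the other way.

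**Conclusion.** The point holds as a gap in prespecification with a modest, conditional cost. The analysis is not committed to factors on which the trial randomises. If only the named covariates are used, and gender or cohort shifts MAIA equally in both arms, the MAIA standard error is somewhat too wide. At 88 analysed this is worth about 1-4 power points for an assumed R² of 10-17%. There is no gain, or about a 1-point loss, at R² of 0, and little or nothing to gain if baseline MAIA is modelled.

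Confidence is high that the covariate list is open, and much lower on the size, which depends on assumed variance shares and on how tightly allocation balances gender within strata.

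**What to change.** In section 9.1, state that the primary MAIA model and the continuous full-sample between-arm models include gender, blood pressure category as randomised, and randomisation cohort as indicators, alongside age and baseline blood pressure. In the same place, specify model-based standard errors, or robust ones with a small-sample correction, and a t reference; without this the added indicators inflate type I error.

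For subgroup or binary outcomes with few participants, adjust for gender and blood pressure category only. Section 9.2 puts alcohol non-adherence at about 15%, or some 15 people in 100, too few to support five or six cohort indicators.

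The cost is a few sentences and about 7-8 degrees of freedom (5 or 6 for cohort, 1 each for gender and blood pressure category), roughly 1 power point if the factors explain nothing. The change does not deal with class clustering confined to the MB-BP arm, which needs its own provision.
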